3.2 Physical Examinations

Physical exam will include both the primary site of the necrotizing soft tissue infection and a clinically appropriate examination of vital organ systems. These include cardiovascular, respiratory, abdomen, extremities, neurologic body systems, and other.

3.3 Concomitant Medication

All concomitant medications antimicrobial & non-antimicrobial will be entered into the CRF and identified by their generic or trade name. Information will include the dose, dosing frequency, route of administration, duration (start and stop dates), and reason for administration. Concomitant medications will be collected up through Day 28.

3.4 Vital Signs

Vital signs include weight, heart rate, systolic and diastolic blood pressure, mean arterial blood pressure (MAP) respiratory rate (spontaneous or controlled) and temperature. While these may be determined many times during the course of the patient hospitalization, recording vital signs in the CRF will be based on once daily readings for specified time sequences according to the time and events schedule.

3.5 Clinical Scores

Clinical scores/criteria components will be collected in the study. APACHE II and LRINEC scores along with Anaya criteria are obtained only at screening while SOFA score is obtained throughout the study. Computational details for all scores are presented in the Appendix 5.

3.5.1 Laboratory Risk Indicator for Necrotizing Fasciitis (LRINEC) score

The LRINEC score (Wong, Khin et al. 2004)⁴ is only obtained at screening and will be used to described baseline disease severity. LRINEC \geq median vs LRINEC < median will be used in the exploratory stratified analyses.

⁴ Wong CH, Khin LW, et al. The LRINEC (Laboratory Risk Indicator for Necrotizing Fasciitis) score: a tool for distinguishing necrotizing fasciitis from other soft tissue infections. Crit Care Med 2004: 32(7): 1535-1541

3.5.2 ANAYA criteria

The ANAYA criteria (Anaya, Bulger et al. 2009) are only obtained at screening and will be used to described baseline severity. ANAYA \geq median vs ANAYA \leq median will be used in the exploratory stratified analyses.

3.5.3 Acute Physiology and Chronic health Evaluation II (APACHE II) score

APACHE II scores are another measure of disease severity to be obtained at screening. APACHE II \geq 10 vs APACHE < 10 will be used in the exploratory stratified analyses.

If there are missing data in the components comprising the APACHE II then some factors may only be evaluable based on medical judgment. If this is the case, Sponsor will provide completed screening APACHE II scores for each randomized patient. If this is the case then the APACHE II scores will not be considered part of the audited clinical data set provided by the data management CRO.

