- APACHE II score, LRINEC and Anaya scores (measurement for these scores will be collected and scores will be calculated retrospectively). The clinical parameters of these scores (respiratory, cardiovascular, vital signs) should be taken as close as possible to the surgery, but prior to the surgical anesthesia or any other surgical related procedures e.g. mechanical ventilation. The worst laboratory values available within 24 hours of surgical intervention for NSTI should be recorded. Critical care parameters (dates and times of assisted ventilation, vasopressor use, ICU and hospital admission and discharge)
- Local lesion assessment and evidence of amputation (excision to a joint space)
- Surgery for NSTI and confirmation of diagnosis. Record time of surgery
- During surgery: Tissue samples for microbiology
- 12 Lead ECG (can be performed any time during screening period or just prior to study drug administration)

- Upon study drug administration patient is transited to visit 2 (either during or after the surgery)
- Collect blood for serum for storage (immunogenicity testing)
- Collect urine and blood for plasma for storage (AKI biomarker analysis)
- Collect whole blood for leukocyte transcriptome (RNA expression) profiling
- Perform randomization

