6.2.8 Clinical Scores

Clinical scores/criteria components will be collected in the study. APACHE II, LRINEC and Anaya score criteria only at screening while mSOFA score throughout the study (see Appendix E, Section 15.5). APACHE II, LRINEC and Anaya criteria will be used to determine disease severity while mSOFA score will be used as a clinical endpoint. Individual parameters of the mSOFA score will be collected and will also be correlated to response. Clinical site personnel will calculate the mSOFA at screening to determine patient eligibility, otherwise all other clinical scores will be calculated retrospectively by the blinded statisticians. (See scores details in Appendix E, Section 15.5). Data will be recorded in the eCRF at specified time points according to time and events Section 15.1.

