9.2.11 Handling Of Missing Data

9.2.11.1 Intent-to-Treat

The purpose of intent-to-Treat comparisons is to ensure that randomization is protected (i.e., all groups have comparable baseline characteristics and that any differences besides therapy are due to chance) and to preclude the possibility of bias due to selectively excluding subjects from therapy groups. This is intended to avoid systematic differences among the groups attributable to factors other than therapy assignment⁴⁸. Therefore, we will attempt to include all randomized patients, regardless of intervention or length of follow-up in the primary efficacy comparison.

9.2.11.2 mSOFA Scores

mSOFA scores will be assessed as 1) observed cases, 2) LOCF, 3) using MMRM, and 4) categorized and combined with mortality and local activity as part of the primary composite clinical success endpoint, NICCE.

Individually missing mSOFA component values due to non-measurement are conventionally assumed as normal and this convention will be followed for this study.

LOCF will not be applied to missing mSOFA scores after patient death in analyses that employ LOCF to describe mean values of time. Therefore, analysis of SOFA mean values using LOCF will focus on morbidity rather than mortality.

Mixed model repeated measures analyses (MRMM) will utilize implicit imputed values for all missing values including those subsequent to patient death.

In categorical analyses including formulation of the primary efficacy endpoint, an mSOFA value that is greater than 1 at Day 14 is considered a treatment failure in the same fashion as patient death. LOCF for SOFA is necessary to guarantee that every patient has a value at Day 14 for use in determining NICCE among patients that are alive at the Day 28 and who have not otherwise failed due to other NICCE components including more than 3 debridements, or amputation beyond the first debridement.

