5.8 Analysis of Longitudinal Outcomes

Supporting analysis will be performed for mSOFA over time using the Mixed Model for Repeated Measures (MMRM) analysis of covariance (ANCOVA) approach¹⁷. The following baseline covariates will be included in the primary MMRM analysis to mSOFA over time.

- Day 0 mSOFA = 3-4 versus > 4
- Presence versus absence of Fournier's gangrene
- APACHE II score
- mSOFA Day 1
- Presence of Stage 2/3 AKI at Screening

mSOFA Day 1 is included because this score reflects patient status post initial surgery. In addition to this variable, the Day 0 stratification factors are included to reflect the experimental design. Screening APACHE II is included to account for variation in medical status at screening. Presence of Stage 2/3 AKI at screening is included given emerging evidence of its impact on clinical outcomes. Inclusion of covariates can increase power by explaining variance and also help with the implicit imputation of missing values that is inherent in the MMRM approach.

MMRM is a direct likelihood approach that requires specialized statistical software for optimizing the likelihood function. For this study, all MMRM parameters will be estimated using SAS PROC MIXED [SAS Institute¹⁸]. The MMRM model is notable for its ability to include all available data from all eligible subjects and does not require their exclusion as in 'complete case analysis'

¹⁵ Cohen, J. Statistical power analysis for the behavioral sciences (2nd ed.). New York, Academic Press, 1988.

¹⁶ Verbeke G and Molenberghs G. Linear Mixed Models for Longitudinal Data, New York: Springer, 2000.

¹⁷ Verbeke G and Molenberghs G. Linear Mixed Models for Longitudinal Data, New York: Springer, 2000.

¹⁸ SAS Institute, Cary NC.

or arbitrary assignment of values as in 'last-observation-carried-forward' (LOCF). The MMRM model generally includes a factor for treatment group by time interaction in order to allow group differences in mean value to vary over time. Inclusion of outcome data from all time points informs the implicit imputation of values missing at specific time points through the outcome covariance matrix. Inclusion of baseline covariates has potential for further reduction of potential bias due from missing values.

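### When APACHE II items are missing, SAP 3.5.3 has the sponsor supply completed, partly judged, unaudited screening scores, with nothing masking the scorer to the post-dose course or locking the score before unblinding

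*SAP*

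**What the plan says.** **Who scores.** Protocol 6.2.8 has site staff calculate the screening mSOFA for eligibility and says that "otherwise all other clinical scores will be calculated retrospectively by the blinded statisticians". Protocol 4.3.1 says of APACHE II, LRINEC and Anaya that "measurement for these scores will be collected and scores will be calculated retrospectively".

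**What happens when items are missing.** SAP 3.5.3 says that if APACHE II components are missing, "some factors may only be evaluable based on medical judgment". In that case the "Sponsor will provide completed screening APACHE II scores for each randomized patient", and "the APACHE II scores will not be considered part of the audited clinical data set provided by the data management CRO".

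**Which text governs.** SAP section 1 says that the SAP prevails where it differs from the protocol.

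**Scoring rules.** SAP 3.5 refers the reader to SAP Appendix 5 for the computation of all scores. That appendix covers LRINEC, Anaya and SOFA and has nothing on APACHE II. The APACHE II table is in protocol Appendix B. It already settles two gaps: GCS counts as normal in a sedated and paralysed patient, and serum HCO3 replaces the oxygenation item when there are no blood gases.

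**Where the score is used.** It is a covariate in the mSOFA MMRM of SAP 5.8 ("Screening APACHE II is included to account for variation in medical status at screening"). It is a candidate covariate in the logistic models of 5.5 and a baseline-balance variable in 5.1. It also defines an exploratory subgroup, at least 10 versus below 10, in 4.6.

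**The concern.** A baseline covariate should be fixed by what was known before treatment. Here the score is completed retrospectively, partly by judgment, by a party that can know how the patient did. A scorer who knows that a patient deteriorated may lean toward a sicker baseline, without intending to. The score then carries part of the outcome, and so part of any treatment effect. Adjusting for it removes some of that effect, and a subgroup cut on it is partly sorted by outcome. Because the cut at 10 is sharp, a few judged points can move a patient across it.

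The departure from the protocol matters even with no leakage. Values set by judgment outside the audited data, with no written rule, cannot be regenerated from the database by program. The plan is stricter with comparable judgments: AKI stage and reference creatinine go to blinded independent adjudicators, debridements to a blinded panel, and ECGs to a blinded central reader.

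**Working it through.** The plan states no figure on this point, so the check is a comparison of texts followed by an illustration of size.

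**1. The texts side by side**

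| Question | Protocol | SAP |
|---|---|---|
| Who calculates APACHE II? | Blinded statisticians (6.2.8) | Sponsor, if components are missing (3.5.3) |
| For whom? | All patients | Each randomized patient, once the rule is triggered |
| By what rule? | Appendix B table with two gap conventions | Medical judgment for some factors; none in Appendix 5 |
| From what data? | Screening; clinical items before anaesthesia (4.3.1); previous 24 hours (Appendix B) | Called a screening score |
| Scorer blind to arm? | Sponsor yes (4.2.1) | Not addressed in 3.5.3 |
| Scorer masked to post-dose course? | Not stated | Not stated |
| Score locked before unblinding? | Not stated | Not stated; only the SAP itself is to be final by then (section 1) |

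The last two rows are the gap. The data window is defined; the procedure that would keep the judgment inside it is not.

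**2. Which analyses the score reaches**

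- NICCE (SAP 2.1.2), CCPE (2.1.3) and the key secondary AKI endpoint (2.3): unadjusted chi-square tests, so not affected.
- mSOFA MMRM: affected. SAP 5.2.4 and 5.8 call it supporting.
- Logistic models in 5.5: affected only if run, since covariates may be assessed there.
- Subgroup tables in 4.6: affected. They are exploratory and cover NICCE, CCPE, mSOFA, critical care, debridements, the AKI endpoint and one adverse-event summary (Table 14.3.1.1).

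**3. Illustrative size**

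All inputs here are assumptions except the 145 patients per arm. Let X be true severity (SD 1), T the arm and Y the outcome (higher is worse):

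Y = 0.5·X − 0.5·T + √(1 − 0.5²)·e

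The recorded score is 6·X (SD 6) plus, in a random share m of patients, k points per SD of Y. Fit Y on T and the recorded score, and compare the coefficient of T with 0.5.

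| Share judged (m) | Shift (k) | Shrinkage of adjusted effect |
|---|---|---|
| 0% | – | about 0% |
| 20% | 2 | 3.2% |
| 20% | 4 | 7.1% |
| 50% | 2 | 9.0% |
| 50% | 4 | 17.9% |

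These come from 3,000 replicates per row; repeat runs agree to within about one percentage point.

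A second set-up has true effect −0.40, slope 0.5, residual SD 0.87 and 2,000 runs. The recorded score is X + λ·(Y − 0.5·X) in the judged share.

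| Share judged | λ = 0 | λ = 0.5 | λ = 1 |
|---|---|---|---|
| 5% | −0.402 | −0.396 | −0.390 |
| 20% | −0.402 | −0.375 | −0.356 |
| 50% | −0.401 | −0.334 | −0.275 |

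The extreme cell, full leakage in half of all patients, is a shrinkage of 1 − 0.275/0.401 = 31%. With no true effect, rejection at a nominal 5% stayed between 4.2% and 5.5% in every cell.

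Both models agree on direction: a scorer blind to arm pulls the estimate toward zero and creates no false positives.

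**The case against.** The strongest reply is that little depends on this. The rule applies only if components are missing. The score is a screening score with a defined window. The sponsor is blind to allocation, so it cannot score by arm. The precedence clause settles which document governs. No confirmatory test uses APACHE II. All of that stands, and it rules out several stronger readings that a reader might infer:

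- *Every score is set by judgment.* The SAP says some factors may need it. The sponsor supplies the completed score for each patient, but that does not make every score a judged one.
- *The plan brings post-dose information into the baseline score.* No section says so, and the score is defined on screening data. Leakage is a possibility left open.
- *The primary result is at risk.* It is not; the test is unadjusted.
- *Nothing could be checked.* The APACHE form is a planned patient listing (16.2.8.20), so a judged score could be compared with recorded components. What is lost is a score derivable by rule from audited data.

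The illustration is also open to criticism. The judged shares and shifts have no source in the documents. The planned MMRM carries further covariates, including Day 1 mSOFA, which is itself measured after dosing, so the percentages do not transfer directly to that model.

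The reply does not close the gap. The precedence clause makes the weaker rule operative without making it sound, and blinding to arm is not masking to clinical course.

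**Conclusion.** The point holds in a limited form. The SAP replaces a calculation by blinded statisticians with sponsor-completed, partly judged, unaudited scores whenever APACHE II items are missing. It does not mask the scorer to the post-dose course or lock the score before unblinding.

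The exposure is confined to the supporting mSOFA MMRM, optional logistic models and exploratory subgroups. If leakage occurred, the adjusted effect would shrink by roughly 3% to 18% when 20% to 50% of patients are judged at 2 to 4 points per SD of outcome. It would shrink less with fewer judged scores, and by up to about 31% under the extreme assumption above. If the judgment uses no post-dose information, there is no shrinkage. The documents give no missing-item rate, so these figures show direction and order of size only. Type I error is not inflated, and the NICCE, CCPE and key secondary AKI conclusions do not depend on the score.

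The change is worth making because a better method is cheap and largely written in the protocol already.

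**What to change.** In SAP 3.5.3 and Appendix 5:

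1. The blinded statisticians derive APACHE II by program from audited pre-dose eCRF values, as protocol 6.2.8 provides.
2. Apply the protocol's Appendix B conventions first: GCS regarded as normal under sedation and paralysis, and serum HCO3 in place of oxygenation when there are no blood gases.
3. Score any item still missing as 0 points, and report the number missing per patient and by arm.
4. Use this score in 4.6, 5.5 and 5.8.
5. Keep any judged score only as a sensitivity analysis, made from pre-dose records without access to post-dose data and locked before unblinding.

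The order of steps 2 and 3 matters. A blanket zero would override the HCO3 rule, and blood gases are drawn only if clinically indicated, so that gap is foreseeable. The zero in step 3 should be stated as a choice for APACHE II and not as the existing mSOFA rule. Protocol 9.2.11.2 does say "Individually missing mSOFA component values due to non-measurement are conventionally assumed as normal", but the governing SAP (5.2 and 5.10.1) uses zero only when a single organ score is missing, and carries earlier values forward (to Day 14) when two or more are missing.

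The cost is SAP wording and one derivation program. The downside is that severity is somewhat understated for patients with missing items, and some may fall below the cut at 10; the reported counts would show how many could be affected.

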3.5.4 Sequential Organ Failure Assessment (SOFA) Score

A modified version of the SOFA score will be used as a clinical end point and will be calculated as described in Section 5.2 and Appendix 5. The modification is that the liver component is not used. Individual parameters of the SOFA score will be collected as summarized as well as the modified SOFA total score (mSOFA). Data will be recorded in the CRF at specified time points according to the time and events schedule. Additionally, SOFA will be computed and described for screening, Day 7, and Day 14. Additional handling of the neuro deficit component is described below.

3.6 Electrocardiogram

12-lead electrocardiogram will be according to time and events schedule. The following parameters will be recorded for each ECG: PR interval, RR interval, QRS complex time, QT interval and Corrected QT interval (QTc). Additionally, descriptive text will be provided for any ECG abnormalities as evaluated by site personnel.

The primary ECG results will be obtained from an independent and blinded cardiology central reader including QTcB and QTcF as well as the measures listed above.

3.7 Clinical Laboratory Assessments

Safety laboratory assessments will be performed according to the to the time and events schedule (See Clinical Study Protocol).

3.8 Microbiology

Microbiological testing will be performed as described in the Clinical Study Protocol and time and events schedule.

3.9 Use of additional concomitant therapy

The following measures of additional medical therapies will be recorded:

- Hyperbaric oxygen
- Intravenous gamma globulin (IVIG)
- Plasmapheresis

4 Secondary and Exploratory Endpoints

4.1 AKI Related Endpoints

4.1.1 Freedom from Durable Loss of Renal Function at Day 28

The same endpoint that is being currently employed in the ongoing ATB-203 study of AKI in sepsis will be the key secondary endpoint in this study. Only subjects with AKI Stage 2 or Stage 3 prior to drug dosing will be included in this comparison.

The key secondary AKI endpoint is *freedom from durable loss of renal function at Day 28* defined as alive, free of dialysis, and less than a 37% loss of estimated Glomerular Filtration Rate (eGFR; measured with the Modification of Diet in Renal Disease (MDRD) formula from the patient's reference eGFR)) at Day 28.

Reference creatinine values, baseline AKI stage and percentage loss of eGFR at Day 14 and 28 will be determined through algorithmic determination (see details below). Percentage loss of eGFR determined algorithmically will be based on a comparison of eGFR at screening compared to an algorithmically determined reference creatinine value. A sensitivity analysis will utilize an independently adjudicated reference value to determine baseline eGFR.

To control type 1 error for the key secondary efficacy endpoint, superiority of Reltecimod relative to placebo in terms of freedom from durable loss of renal function among those with Stage 2 or Stage 3 AKI prior to dosing, will only be interpreted as a confirmatory hypothesis test if p \leq 0.01 for the primary endpoint (NICCE) and p \leq 0.05 for the co-primary endpoint (CPEP). Otherwise, treatment group comparisons in terms of the key secondary efficacy (AKI) endpoint will be interpreted as a descriptive endpoint. An unadjusted chi-square test using a two-sided type 1 error of α =0.05 will be used to test superiority of Reltecimod relative to placebo for the key secondary AKI endpoint.

4.1.2 Blinded Independently Adjudicated AKI Endpoints and Analyses

Reference creatinine values, maximal AKI stage, and AKD stage at Day 14 will be determined by a blinded independent adjudication committee as described in the Clinical Study Protocol. AKI Stage assigned through blinded independent adjudication will be for Maximal stage by KDIGO criteria using creatinine and/or urine output over the first 7 days post screening. For these analyses, subjects with a maximal AKI Stage 2 or AKI Stage 3 will be included. Descriptive comparisons will be made between the Screening (pre-dose) AKI stage and Maximal AKI stage and between the Day 14 algorithmically determined endpoints to the Day 14 independently adjudicated endpoint.

4.1.3 Other AKI Endpoints

Exploratory AKI endpoints include the primary endpoint evaluated at Day 14, improvement in durable loss of renal function defined as alive, free of dialysis and improvement leading to a lower AKI stage but no better than Stage 1 AKI evaluated at Day 14 and Day 28, and AKD stage evaluated at Day 14 and Day 28.

